#### 6.3.2 Survival Follow-Up

All patients will be contacted for survival every 12 weeks ( $\pm$  14 days) following Follow-Up Visit 2 (or following last contact with the patient, if Follow-Up Visit 2 is missed) as follows:

- Survival visits may be conducted in person or by telephone.
- The Sponsor may request that survival data be collected on all treated patients outside of the scheduled contacts. At the time of this request, each patient will be contacted to determine their survival status unless the patient has withdrawn consent for all contact or is lost to follow-up (as defined in Section 6.2.7). Alternative methods to determine survival status may be used (eg, access to medical records and public record searches) as allowed by local regulations and/or guidelines.
- For patients who discontinue study treatment before BICR-confirmed disease progression, radiographic tumor assessments will continue to be collected every 6 weeks ( $\pm$  7 days) or more frequently if clinically indicated. One year after randomization, radiographic tumor assessments will continue to be collected every 9 weeks ( $\pm$  14 days) until BICR-confirmed disease progression, patient withdraws consent, death, initiation of subsequent anticancer therapy, or study termination by the Sponsor.

- Additional subsequent cancer therapy details such as regimen, setting of the regimen, line of therapy, start date and end date of each regimen, best response to the regimen, and date of progression after next line of therapy will be collected.
- Survival follow up should continue until patient withdrawal of consent for survival follow-up, death, loss to follow-up, or study termination by the Sponsor.

## 6.4 End of Study

End of study is defined as no more than 5 years after the last patient received their first dose of study drug or Sponsor decision to terminate the study, whichever comes first.

## 6.5 Dose Modification and Management of Specific Adverse Events

Every effort should be made to follow planned dosing schedules for all study drugs in both treatment arms. Study drug administration may be delayed or modified for toxicity as described below and must be discontinued as required by criteria described in Section 6.6.

For patients in Arm A (bempegaldesleukin plus pembrolizumab): Dose modification for bempegaldesleukin in Arm A may be considered independently from pembrolizumab based on Investigator assessment of relationship of a toxicity to each of the study drugs. If only one of the study drugs meets the criteria for dose delay, then administration of the other study drug may be continued or delayed at the discretion of the Investigator. Likewise, in the event that one of the study drugs in Arm A is permanently discontinued due to toxicities, the other can continue to be administered.

Patients who require a dose delay of pembrolizumab or bempegaldesleukin should be re-evaluated weekly or more frequently if clinically indicated and should resume treatment with combination of bempegaldesleukin and pembrolizumab when retreatment criteria are met. Immuno-oncology agents are associated with AEs that can differ in severity and duration from AEs caused by other therapeutic classes. Early recognition and management of AEs associated with immuno-oncology agents may mitigate severe toxicity.

Tumor assessments for all patients should continue as per protocol even if dosing is delayed.

### 6.5.1 Bempegaldesleukin

#### 6.5.1.1 Monitoring and Management of Specific Adverse Events

##### 6.5.1.1.1 Infusion Reactions

Infusion reactions have been reported during infusions with bempegaldesleukin. If such a reaction were to occur with the bempegaldesleukin infusion, it might manifest with fever, chills, rigors, headache, rash, pruritus, arthralgias, hypotension, hypertension, bronchospasm, or other allergic-like reactions.

Dose modification and toxicity management guidelines for bempegaldesleukin infusions should follow those provided for pembrolizumab infusion reactions that are provided in [Table 5](#) (Section [6.5.2.1.1](#)). For patients randomized to Arm A receiving bempegaldesleukin, note:

- In case of late-occurring hypersensitivity symptoms (eg, appearance of a localized or generalized pruritus within 1 week after treatment), symptomatic treatment may be given (eg, oral antihistamine or corticosteroids).
- If a patient has experienced a previous infusion reaction to bempegaldesleukin, subsequent doses of bempegaldesleukin may be administered at a reduced rate (over longer duration) per Investigator discretion (eg, 50% of the initial rate of infusion). The investigator may also consider re-elevating the rate of infusion if the patient tolerates the subsequent dose(s) well. The Investigator may consult with the Medical Monitor for additional guidance, as needed. Completion of bempegaldesleukin administration must occur within accepted timeframes (eg, from reconstitution or from time bempegaldesleukin is brought to room temperature) as described in the Pharmacy Manual.

#### **6.5.1.1.2 Elevated Hepatic Transaminases: Monitoring and Management**

Elevated hepatic transaminases are a toxicity that can occur for bempegaldesleukin. The elevations in hepatic transaminases associated with bempegaldesleukin typically occur at the time of peak of bempegaldesleukin active metabolite concentrations in the blood (Days 4-8), and are often accompanied by other cytokine-related toxicities such as flu-like symptoms, rash or pruritus. The transient elevations in hepatic transaminases are usually mild or moderate in severity, not associated with increased total bilirubin, resolve spontaneously without treatment, and predominantly occur in Cycle 1 and Cycle 2.

**The following recommendations are for patients randomized to Arm A receiving bempegaldesleukin and apply to Cycle 1 only.** Patients on subsequent cycles of bempegaldesleukin should follow the guidance in [Table 6](#) (Section [6.5.2.1.2](#)). These recommendations are not intended to serve as rigid guidelines or to replace clinical judgment, and do not apply to patients receiving pembrolizumab monotherapy. Hepatic events, including elevated liver function tests, have also been observed for pembrolizumab; for patients receiving pembrolizumab monotherapy, see [Table 6](#) (Section [6.5.2.1.2](#)).

For patients experiencing elevated hepatic transaminases while receiving Cycle 1 of bempegaldesleukin alone or in combination with pembrolizumab, first rule out non-inflammatory etiologies. If non-inflammatory cause, treat accordingly and continue bempegaldesleukin. Consider imaging if obstruction is suspected.

If during monitoring alanine transaminase (ALT)/aspartate transaminase (AST) increases, follow the guidance for the highest levels.

**AST or ALT > 3.0 to  $\leq$  5.0  $\times$  upper limit of normal (ULN)**

Increase frequency of liver function test monitoring to approximately every 3 days and delay treatment until lab abnormalities resolve to Grade 0-1.

If no improvement within 7 days, treat with 0.5 to 1 mg/kg/day prednisone equivalents, and taper steroids over at least 1 month before resuming treatment.

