**ALT or AST > 5.0 to  $\leq$  8.0  $\times$  ULN**

Increase frequency of monitoring to approximately every 3 days until lab abnormalities resolve to Grade 0-1.

Treatment must be delayed until lab abnormalities resolve to Grade 0-1.

If no improvement within 7 days:

- Discontinue bempegaldesleukin and pembrolizumab
- 1 to 2 mg/kg/day prednisone equivalents followed by corticosteroid taper over at least one month
- Consult gastroenterologist
- Consider adding non-corticosteroid immunosuppressive medication if no improvement in > 3-5 days, worsens or rebounds while on steroids

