### 6.5.2.1.2 Immune-related AEs Associated with Pembrolizumab

AEs associated with pembrolizumab exposure may represent an immune-related response. These irAEs may occur shortly after the first dose or several months after the last dose of pembrolizumab treatment and may affect more than one body system simultaneously. Therefore, early recognition and initiation of treatment is critical to reduce complications. Based on existing clinical study data, most irAEs were reversible and could be managed with interruptions of pembrolizumab, administration of corticosteroids and/or other supportive care. For suspected irAEs, ensure adequate evaluation to confirm etiology or exclude other causes. Additional procedures or tests such as bronchoscopy, endoscopy, skin biopsy may be included as part of the evaluation.

Dose modification and toxicity management guidelines for irAEs associated with pembrolizumab are provided in [Table 6](#). These guidelines apply to patients **receiving bempegaldesleukin in combination with pembrolizumab OR either treatment as a monotherapy**.

For toxicities requiring treatment discontinuation, bempegaldesleukin or pembrolizumab alone may continue as a monotherapy if the toxicity is considered not related to that study drug by the Investigator.

**For patients in Arm A receiving bempegaldesleukin**, elevations of AST or ALT occurring in Cycle 1 should be managed according to the guidelines in Section [6.5.1.1.2](#). For elevations of AST or ALT occurring in Cycle 2 or beyond, follow the dose modification and toxicity management guidelines in [Table 6](#).

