**Note: Non-irAE will be managed as appropriate, following clinical practice recommendations.**

- a. AST/ALT:  $> 3.0 - 5.0 \times \text{ULN}$  if baseline normal;  $> 3.0 - 5.0 \times \text{baseline}$ , if baseline abnormal;  
bilirubin:  $> 1.5 - 3.0 \times \text{ULN}$  if baseline normal;  $> 1.5 - 3.0 \times \text{baseline}$  if baseline abnormal
- b. AST/ALT:  $> 5.0$  to  $20.0 \times \text{ULN}$ , if baseline normal;  $> 5.0 - 20.0 \times \text{baseline}$ , if baseline abnormal;  
bilirubin:  $> 3.0 - 10.0 \times \text{ULN}$  if baseline normal;  $> 3.0 - 10.0 \times \text{baseline}$  if baseline abnormal
- c. AST/ALT:  $> 20.0 \times \text{ULN}$ , if baseline normal;  $> 20.0 \times \text{baseline}$ , if baseline abnormal;  
bilirubin:  $> 10.0 \times \text{ULN}$  if baseline normal;  $> 10.0 \times \text{baseline}$  if baseline abnormal
- d. The decision to withhold or permanently discontinue study treatment is at the discretion of the investigator or treating physician. If control achieved or  $\leq$  Grade 2, study treatment may be resumed.
- e. Events that require discontinuation include but are not limited to: encephalitis and other clinically important irAEs (eg, vasculitis, sclerosing cholangitis).
- f. For patients in Arm A receiving bempegaldesleukin in Cycle 1, consult the guidelines in Section [6.5.1.1.2](#).

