## 10.3 Grading of AEs

The severity of an event and the seriousness are not to be considered synonymous. The severity is grading the intensity of an event. The seriousness of event is based on the patient/event outcome or action criteria. All AEs will be assessed for severity using the National Cancer Institute Common Terminology Criteria for Adverse Events (NCI-CTCAE) version 5.0 guidelines. If a particular AE is not listed in the NCI-CTCAE, the following criteria will be used:

- Grade 1 = Mild (event results in mild or transient discomfort, not requiring or needing only minimal intervention or treatment; does not limit or interfere with daily activities [eg, insomnia, mild headache]).

- Grade 2 = Moderate (event is sufficiently discomforting so as to limit or interfere with daily activities; may require interventional treatment [eg, fever requiring antipyretic medication]).
- Grade 3 = Severe (event results in significant symptoms that prevent normal daily activities; may require hospitalization or invasive intervention).
- Grade 4 = Life threatening or disabling.
- Grade 5 = Death.

AEs will be reported with an individual start and stop date for each level of severity.

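### In Arm A, Cycle 1, AST/ALT delay bands are set in multiples of ULN but the delay ends by grade, so with an abnormal baseline some on-treatment values meet both the delay and the release condition

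*Protocol*

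**What the plan says.** - **Eligibility.** Protocol Section 5.1, inclusion criterion 9, allows AST or ALT up to 2.5 x ULN. A patient can therefore enter with a value above normal.
- **Cycle 1 delay, lower band.** Section 6.5.1.1.2, for values above 3.0 and up to 5.0 x ULN: "delay treatment until lab abnormalities resolve to Grade 0-1".
- **Cycle 1 delay, upper band.** The same section, for values above 5.0 and up to 8.0 x ULN: "Treatment must be delayed until lab abnormalities resolve to Grade 0-1".
- **Grading system.** Section 10.3: "All AEs will be assessed for severity using the National Cancer Institute Common Terminology Criteria for Adverse Events (NCI-CTCAE) version 5.0 guidelines". Table 6 carries the same CTCAE version in its grade column.
- **Grade limits.** Footnotes a to c of Table 6 (Section 6.5.2.1.2) are the only place where AST/ALT grades are given numbers. Grade 2 begins above 3.0 x ULN when baseline is normal, and above 3.0 x baseline "if baseline abnormal".

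Section 6.5.1.1.2 makes no adjustment of its delay bands for baseline. It also does not say how Grade 0-1 is to be read when baseline is raised.

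**The concern.** A rule for holding a drug needs an entry condition and an exit condition that cannot both be true of one measurement. Here the entry condition is on the ULN scale. The exit condition is on the grade scale, which changes its reference from ULN to baseline for patients who start above normal. Where the two scales part, one liver value gives two incompatible instructions: treatment is to be delayed, and the condition for ending the delay is already satisfied.

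Two sites with identical laboratory results could then act differently on dosing, each following the text. That bears on patient safety and on how consistently early exposure in Arm A is determined.

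**Working it through.** The plan states no figure to reproduce; the check is on thresholds.

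**Notation.** b = baseline AST or ALT, and x = on-treatment Cycle 1 value, both in multiples of ULN. Eligibility requires b ≤ 2.5.

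**Conditions.**
- Delay (Section 6.5.1.1.2, both bands together): 3.0 < x ≤ 8.0.
- Release (Grade 0-1, that is, below the start of Grade 2 in footnote a): x ≤ 3.0 if baseline is normal; x ≤ 3.0 x b if baseline is abnormal (b > 1).

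Grade 1 is not itself given numbers; its upper limit is taken from where Grade 2 begins.

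**Normal baseline.** Delay needs x > 3.0 and release needs x ≤ 3.0. No value satisfies both, so the rule works as written.

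**Abnormal baseline.** Both conditions hold when 3.0 < x ≤ 3.0 x b. With b at most 2.5, the upper end is at most 3.0 x 2.5 = 7.5, which lies inside the delay bands.

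| Baseline b (x ULN) | 3.0 x b | Values meeting both conditions (x ULN) |
|---|---|---|
| 1.0 (normal) | – | none |
| 1.1 | 3.3 | > 3.0 to 3.3 |
| 1.5 | 4.5 | > 3.0 to 4.5 |
| 1.67 | 5.0 | > 3.0 to 5.0, the whole lower band |
| 2.0 | 6.0 | > 3.0 to 6.0 |
| 2.5 (entry limit) | 7.5 | > 3.0 to 7.5, the lower band and most of the upper |

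**Single values.**
- b = 2.0, x = 3.5: 3.5 / 2.0 = 1.75 x baseline. This is below Grade 2, yet in the lower delay band.
- b = 2.5, x = 6.0: 6.0 / 2.5 = 2.4 x baseline. This is below Grade 2, yet in the upper band, where delay is mandatory.

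**Check on the cause.** If delay and release used one reference, either ULN for both or baseline for both when baseline is abnormal, each cut would sit at 3.0 times that reference and the overlap would be empty for every b. The mismatch of references is the whole source of the conflict.

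**The case against.** **The Cycle 1 text is guidance.** Section 6.5.1.1.2 describes its recommendations as flexible and subordinate to clinical judgement, and a site is unlikely to regard a value that has just triggered a delay as resolved. This softens the conflict. It does not say which reference applies, and the upper band is worded as an obligation. The general rule in Section 6.5.1.2, which allows resumption at Grade 1 or below or on return to baseline, does not settle the reference either.

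**Table 6 does not govern Cycle 1.** Its actions do not. But the Cycle 1 release condition is written in grades, and the footnotes are the only AST/ALT grade definitions in the protocol.

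**Timing.** Section 6.5.1.1.2 places typical elevations at Days 4 to 8, well before the next three-weekly dose. The release wording therefore matters mainly when an elevation persists. That limits frequency but does not remove the contradiction.

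Four stronger readings are tempting, and the documents do not support them:

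- *Every patient entering with raised AST/ALT is caught.* The on-treatment value must fall inside the window, which at b = 1.1 is only 3.0 to 3.3 x ULN.
- *Cycle 1 and later cycles contradict each other.* The split is deliberate and explained: "For elevations of AST or ALT occurring in Cycle 2 or beyond, follow the dose modification and toxicity management guidelines in" Table 6. Different rules for two declared periods are not an inconsistency.
- *Cycle 1 is stricter than Table 6 for all abnormal baselines.* At b = 1.1, 7.0 x ULN is 7.0 / 1.1 = 6.4 x baseline. That is Grade 3, for which Table 6 requires permanent discontinuation while Cycle 1 begins with a delay.
- *Loss of both drugs in Cycle 1 turns on the scale a site uses.* The Cycle 1 AST/ALT triggers for stopping both drugs are expressly in ULN and contain no grade.

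**Conclusion.** The concern holds in a limited form. For an eligible Arm A patient with abnormal baseline b (1 < b ≤ 2.5), a Cycle 1 AST or ALT above 3.0 x ULN and at or below 3.0 x b x ULN meets both the delay rule and its release condition. The window exists for every abnormal baseline and widens with b, reaching 7.5 x ULN at the entry limit. With a normal baseline there is none.

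The conclusion assumes that Grade 0-1 in Section 6.5.1.1.2 is read through the Table 6 footnotes, and that Grade 1 ends where Grade 2 begins.

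The number of patients affected cannot be derived. It would be the Arm A number (250 planned) x the share with abnormal baseline x the chance that such a patient has a Cycle 1 value in the window, and the documents give neither of the last two factors. Counting every patient with a raised baseline would give those at risk, not those affected. The SAP reports that the trial was discontinued after one patient was enrolled, so the practical effect here is small. The defect in the text remains for any reuse of these rules.

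**What to change.** Reconcile the two delay bands of Section 6.5.1.1.2 with footnotes a to c of Table 6. State which reference, ULN or baseline, defines Grade 0-1 in that section for a patient whose baseline AST or ALT is abnormal, so that the delay and release conditions cannot both be met by one value. Section 6.5.2.1.3 already sets AST/ALT criteria that name their reference by baseline level, so the protocol has a model for this wording. The sponsor must decide which reference applies; no threshold or management rule is proposed here.

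The cost is a wording change in one section, with a matching table footnote if needed. It touches no sample size, endpoint or analysis.

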**ALT or AST > 5.0 to  $\leq$  8.0  $\times$  ULN**

Increase frequency of monitoring to approximately every 3 days until lab abnormalities resolve to Grade 0-1.

Treatment must be delayed until lab abnormalities resolve to Grade 0-1.

If no improvement within 7 days:

- Discontinue bempegaldesleukin and pembrolizumab
- 1 to 2 mg/kg/day prednisone equivalents followed by corticosteroid taper over at least one month
- Consult gastroenterologist
- Consider adding non-corticosteroid immunosuppressive medication if no improvement in > 3-5 days, worsens or rebounds while on steroids

**ALT or AST > 8.0  $\times$  ULN**

- Discontinue bempegaldesleukin and pembrolizumab
- Increase frequency of monitoring to approximately 1-2 days
- 1 to 2 mg/kg/day prednisone equivalents followed by corticosteroid taper over at least one month
- Consult gastroenterologist
- If no improvement in > 3–5 days, worsens or rebounds, add non-corticosteroid immunosuppressive medication
- Additional guidance is provided in [Table 6](#) (Section 6.5.2.1.2)

Additionally, any bempegaldesleukin-related liver function test abnormality that meets the following criteria requires discontinuation of bempegaldesleukin:

- Total bilirubin > 5  $\times$  ULN
- Concurrent AST or ALT > 3  $\times$  ULN and total bilirubin > 2  $\times$  ULN

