**Table 6: Dose Modification and Toxicity Management Guidelines for Immune-Related AEs Associated with Study Treatment**

General instructions:				

 
1. Severe and life-threatening irAEs should be treated with IV corticosteroids followed by oral steroids. Other immunosuppressive treatment should begin if the irAEs are not controlled by corticosteroids.
 
2. Study treatment must be permanently discontinued if the irAE does not resolve or the corticosteroid dose is not <math>\leq 10</math> mg/day within 12 weeks of the last treatment.
 
3. The corticosteroid taper should begin when the irAE is <math>\leq</math> Grade 1 and continue at least 4 weeks.
 
4. If study treatment has been withheld, treatment may resume after the irAE decreased to <math>\leq</math> Grade 1 after corticosteroid taper.
 
				
irAEs	Toxicity Grade (CTCAE v5.0)	Action with Study Treatment	Corticosteroid and/or Other Therapies	Monitoring and Follow-Up
Pneumonitis	Grade 2	Withhold	
 
• Administer corticosteroids (initial dose of 1 - 2 mg/kg prednisone or equivalent) followed by taper
 
• Add prophylactic antibiotics for opportunistic infections
 
	
 
• Monitor patients for signs and symptoms of pneumonitis
 
• Evaluate patients with suspected pneumonitis with radiographic imaging and initiate corticosteroid treatment
 

	Recurrent Grade 2, Grade 3 or 4	Permanently discontinue		

irAEs	Toxicity Grade (CTCAE v5.0)	Action with Study Treatment	Corticosteroid and/or Other Therapies	Monitoring and Follow-Up
Diarrhea / Colitis	Grade 2 or 3	Withhold	
 
Administer corticosteroids (initial dose of 1 - 2 mg/kg prednisone or equivalent) followed by taper
 
	
 
Monitor patients for signs and symptoms of enterocolitis (ie, diarrhea, abdominal pain, blood or mucus in stool with or without fever) and of bowel perforation (ie, peritoneal signs and ileus)
 
Patients with <math>\geq</math>Grade 2 diarrhea suspecting colitis should consider GI consultation and performing endoscopy to rule out colitis
 
Patients with diarrhea/colitis should be advised to drink liberal quantities of clear fluids. If sufficient oral fluid intake is not feasible, fluid and electrolytes should be substituted via IV infusion
 

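### The bempegaldesleukin stop rule for combined transaminase and bilirubin rises sits only in the Cycle 1 liver section, and Table 6, which governs later cycles, has no matching criterion

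*Protocol*

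**What the plan says.** Protocol Section 6.5.1.1.2 opens its guidance with a scope statement: "The following recommendations are for patients randomized to Arm A receiving bempegaldesleukin and apply to Cycle 1 only". It adds: "These recommendations are not intended to serve as rigid guidelines or to replace clinical judgment". For later cycles: "Patients on subsequent cycles of bempegaldesleukin should follow the guidance in" Table 6. Section 6.5.2.1.2 repeats the direction: "For elevations of AST or ALT occurring in Cycle 2 or beyond, follow the dose modification and toxicity management guidelines in" Table 6.

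After the AST/ALT bands, Section 6.5.1.1.2 closes with a separate paragraph: "any bempegaldesleukin-related liver function test abnormality that meets the following criteria requires discontinuation of bempegaldesleukin". Two criteria follow:

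- total bilirubin > 5 × ULN;
- AST or ALT > 3 × ULN concurrent with total bilirubin > 2 × ULN.

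No cycle is stated in that paragraph.

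The Table 6 liver row withholds treatment at Grade 2 and stops it permanently at Grade 3 or 4. AST/ALT and bilirubin are graded separately, against ULN if baseline is normal and against baseline if it is abnormal (footnotes a to c). Footnote f points back to Section 6.5.1.1.2 for Cycle 1 only. On resumption, Table 6 says: "If study treatment has been withheld, treatment may resume after the irAE decreased to" Grade 1 or lower, following the steroid taper.

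The bempegaldesleukin discontinuation list in Section 6.5.1.3 neither contains the two criteria nor refers to Section 6.5.1.1.2. Section 6.6 points only to Sections 6.5.1.3 and 6.5.2.1.

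**The concern.** A mandatory hepatic stop rule should say which cycles it covers and should appear in the list that investigators consult when deciding whether to stop. This one does neither. An investigator following the directions for Cycle 2 onward could withhold bempegaldesleukin and later resume it after a pattern that another part of the protocol says requires discontinuation. A colleague who reads the closing sentence as covering all cycles would stop the drug. With about 225 planned sites, the same liver result could be handled in two ways.

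The timing matters. Section 6.5.1.1.2 says that bempegaldesleukin transaminase elevations occur predominantly in Cycles 1 and 2, and Cycle 2 already falls under Table 6. The section also says that the usual transient elevations come without a rise in total bilirubin, so the combined pattern is what marks a case out from the expected one.

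**Working it through.** The protocol gives no figure to reproduce. The check compares thresholds, all in × ULN unless stated. Inputs are Section 6.5.1.1.2, Table 6 with footnotes a to c, and inclusion criterion 9 in Section 5.1 (AST or ALT ≤ 2.5; total bilirubin ≤ 1.5, or above that if direct bilirubin ≤ ULN).

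**Normal baseline.** Table 6 Grade 2 is AST/ALT > 3.0–5.0 or bilirubin > 1.5–3.0; Grade 3 starts above 5.0 and 3.0 respectively.

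| Finding | Section 6.5.1.1.2 | Table 6 |
|---|---|---|
| AST/ALT > 3–5 alone | delay; steroids if no improvement in 7 days | withhold, steroids |
| AST/ALT > 5–8 alone | delay; stop if no improvement in 7 days | permanent stop |
| AST/ALT > 8 | stop | permanent stop |
| Bilirubin > 3–5 alone | no rule | permanent stop |
| Bilirubin > 5 | stop | permanent stop |
| AST/ALT > 3–5 with bilirubin > 2–3 | stop | withhold, steroids; may resume |

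Only in the last row is Table 6 the looser rule. Example: AST 4 and bilirubin 2.5 meet the combined criterion (4 > 3 and 2.5 > 2), but both values are Grade 2 in Table 6. Above either upper limit, Table 6 also stops permanently. For AST/ALT > 5–8 alone, Table 6 is stricter than the Cycle 1 text, which says: "Treatment must be delayed until lab abnormalities resolve to Grade 0-1".

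**Abnormal baseline, combined criterion.** Grade 2 becomes 3.0–5.0 × baseline for AST/ALT and 1.5–3.0 × baseline for bilirubin.

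- AST/ALT baseline 1.5, 2.0, 2.5: Grade 2 is > 4.5–7.5, > 6–10, > 7.5–12.5.
- Bilirubin baseline 1.2, 1.5: Grade 2 is > 1.8–3.6, > 2.25–4.5.

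Table 6 does not stop treatment permanently until one test passes its Grade 2 upper limit. With baselines of 2.5 and 1.5, the two rules therefore differ for AST/ALT > 3 to 12.5 with bilirubin > 2 to 4.5.

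There is also a corner below Grade 2 on both tests, where the Table 6 liver row calls for no action. For bilirubin it needs 1.5 × baseline > 2, so baseline > 2/1.5 = 1.33. For AST/ALT it needs 3 × baseline > 3, so baseline > 1.0. Example: baselines of AST 2.4 and bilirubin 1.4 put the Grade 2 thresholds at 3 × 2.4 = 7.2 and 1.5 × 1.4 = 2.1. A rise to 3.1 and 2.05 meets the combined criterion but reaches neither threshold. For patients enrolled with total bilirubin ≤ 1.5, the corner spans at most bilirubin > 2.0 to 1.5 × 1.5 = 2.25.

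**Abnormal baseline, bilirubin > 5 criterion.** Table 6 is looser only if 3.0 × baseline > 5, so baseline > 5/3 = 1.67. That baseline is eligible only by the direct-bilirubin route. At baseline 2.0, withholding runs to 3 × 2.0 = 6.0, so the rules differ for bilirubin > 5 to 6.0.

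**The case against.** The strongest reply is that the rule already covers every cycle. The Cycle 1 limit is attached to recommendations described as not rigid. The closing paragraph is separate, is worded as a requirement, and reaches any bempegaldesleukin-related abnormality. Table 6 manages immune-related events and does not say that it overrides a drug-specific stop rule, so both can apply. This reading is plausible. A reader might infer that no stop rule for the pattern exists after Cycle 1; the documents do not support that, and the defect is unclear scope and placement. The other reading nevertheless remains open, because the paragraph closes a section confined to Cycle 1, two passages redirect later cycles, and footnote f points back for Cycle 1 only.

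The second reply is that the affected band is already managed, and much of this stands. With normal baseline, Table 6 requires withholding and steroids, and the taper lasts at least 4 weeks. "Study treatment must be permanently discontinued if the irAE does not resolve or the corticosteroid dose is not" 10 mg/day or lower within 12 weeks of the last treatment. Section 6.5.1.2 excepts resumption where recurrence would pose undue risk, and Section 6.5.1.3 calls for stopping when the investigator judges the clinical risk substantial. Sections 10.13 and 10.14 require causality assessment and SAE reporting, with no cycle limit, for a near-identical pattern (AST/ALT ≥ 3, bilirubin ≥ 2, alkaline phosphatase < 2, all × ULN). None of these names the combined pattern as a reason to stop, and reporting is not a dosing action.

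A reader might also infer that Table 6 is generally laxer than the Cycle 1 guidance. With normal baseline it is stricter for isolated AST/ALT > 5–8 × ULN and for isolated bilirubin > 3–5 × ULN.

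**Conclusion.** The point holds as an ambiguity of scope with a narrow safety consequence. If the closing paragraph is read as Cycle 1 only, the later-cycle guidance is looser, with normal baseline, only for AST/ALT > 3–5 × ULN with bilirubin > 2–3 × ULN. With abnormal baseline the band is somewhat wider, and the part with no action in the Table 6 liver row is small for patients enrolled with total bilirubin ≤ 1.5 × ULN. If the paragraph is read as covering all cycles, the dosing rule is complete but misplaced.

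The comparison assumes an abnormality judged related to bempegaldesleukin and an eligible baseline. The documents give no rate for the combined pattern. Their statement that transaminase rises usually come without raised bilirubin suggests that it would be uncommon, so no number of affected patients can be inferred.

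The SAP records that the trial was discontinued with one patient enrolled and treated, so the benefit within this trial is small; the correction matters mainly if the liver section is reused. Severity: minor safety clarification.

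**What to change.** Make three linked edits:

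1. Insert *in any cycle* in the closing sentence of Section 6.5.1.1.2, so that both criteria plainly apply throughout treatment.
2. List both criteria in Section 6.5.1.3 as permanent bempegaldesleukin discontinuation criteria. This also covers the corner below Grade 2.
3. Add a footnote to the Table 6 liver row, stated in × ULN, saying that these criteria take precedence over Grade 2 withholding.

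No separate exception is needed for patients enrolled with raised total bilirubin and normal direct bilirubin: the existing condition that the abnormality be bempegaldesleukin-related lets a stable raised baseline be discounted.

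The cost is a few lines of text. Appendix 1B already requires AST, ALT and total bilirubin before each bempegaldesleukin dose. The downside is that a few more patients may stop bempegaldesleukin; under Section 6.5.1.3 pembrolizumab may continue alone if the investigator judges the toxicity unrelated to it.
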